A phase I/II clinical trial has completed subject accrual in subjects with non-castrate, non-metastatic prostate cancer. The primary objectives of that trial were to evaluate the safety and immunological efficacy of the same pTVG-HP DNA vaccine encoding hPAP when administered to patients with clinical stage D0 prostate cancer [60]. This was a dose-escalation study, with an expanded cohort of subjects treated at the maximum tolerated dose. In the dose-escalation portion, nine subjects were treated in three dose cohorts of 100 μ g, 500 μ g, or 1500 μ g DNA, administered intradermally every two weeks for six total immunizations. 200 μ g GM-CSF was co-administered as a vaccine adjuvant with each immunization. 13 additional subjects were treated in an expanded cohort at the 1500 μ g DNA dose. Safety evaluation included monthly blood tests (CBC, creatinine, urinalysis, anti-nuclear antibody tests, liver function tests, and serum amylase) and physical examination and review of systems. Subjects were also monitored for one hour after each vaccination for any immediate allergic reactions. No serious adverse events were observed, and no significant laboratory anomalies were observed apart from a single grade 3 amylase that was assessed to not be treatment-related. No other events > grade 2 were observed in any of the 22 subjects treated. Common events observed have been grade 1/2 fevers, chills, and local site reactions lasting typically less than 24 hours. 2/22 subjects experienced grade 2 back pain occurring \sim 45 minutes after treatment and lasting < 10 minutes.

The primary immunological endpoint of this trial was the induction of PAP-specific IFN γ -secreting effector CD8+ T cells detectable two weeks following the final immunization. For this evaluation all study subjects underwent leukapheresis within two weeks before beginning the 12-

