week immunization series and again two weeks after the final immunization. With the leukapheresis products, autologous dendritic cells were prepared by culture of flask-adherent monocytes for six days in serum-free medium supplemented with GM-CSF and IL-4. CD8+ T cells, purified from PBMC by negative magnetic bead selection, were cultured with autologous dendritic cells and protein antigens for 96 hours, without *in vitro* restimulation, and ELISPOT was used as a quantitative direct assessment of effector T-cell response. As shown in Figure 6, three patients had a significant increase in the number of PAP-specific IFN γ -secreting CD8+ T cells after immunization compared with pre-immunization, one patient from each dose cohort. In addition, several subjects, including the subject with the greatest magnitude ELISPOT response, were also found to have PAP-specific memory T-cell recall responses as identified by proliferating CD4+ and CD8+ T cells in a 96-hour proliferation assay following antigen-stimulation (Figure 7). Finally, several individuals experienced a prolongation in PSA doubling time over one year following treatment compared with pre-treatment. Overall the median PSA doubling time was 6.5 months in the four months pre-treatment and 8.5 months in the 4-month on-treatment period ($p = 0.033$). Long-term PAP-specific IFN γ -secreting T-cell responses were observed in several patients up to one year after immunization. In addition, one patient went on to receive booster immunizations with 100 μ g pTGV-HP at monthly intervals. As shown in Figure 8, booster immunizations were able to augment PAP-specific CD4+ and CD8+ proliferative T cells, as well as PAP epitope-specific CD8+ T cells (Figure 9) months after the initial immunization course. Taken together, these results demonstrate that pTGV-HP can elicit PAP-specific T-cell immune responses, CD8+ T-cell responses in particular, and these responses could be elicited at even the lowest dose (100 μ g) of plasmid DNA vaccine tested. In subsequent studies, we have further found that PAP-specific IFN γ responses were detectable in several individuals at multiple time points after immunization, and the presence of this persistent immunity was associated with favorable changes in PSA doubling time. These results, demonstrating immunological efficacy with the 100 μ g dose, and safety in at least one individual with ongoing immunization at that dose, form the basis of the current trial design using a similar vaccination induction schedule, but continuing with periodic (quarterly) booster immunizations.

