1. Physical examination, including vital signs, symptoms assessment, and ECOG performance score (not required if already obtained within 14 days)
2. Blood draw for serum PSA and PAP (to be obtained prior to administration of immunization/GM-CSF). May be done up to 3 days in advance of Day 1.
3. Immunization as described in sections 6 and 8 above. Specifically, subjects will receive immunizations intradermally on the deltoid area of the lateral arm (preferentially left arm) with 0.25 cc administered at each of two adjacent sites.
4. Following vaccinations, the subjects will be observed for 60 minutes for unanticipated adverse events.

D. Second, third, fifth and sixth biweekly treatment visits (days 15, 29, 57 and 71, each +/- 2 days)

1. Symptoms assessment
2. Immunization/GM-CSF and post-treatment monitoring as described above

E. Fourth immunization/GM-CSF treatment visit (day 43 +/- 2 days)

1. Physical examination, including vital signs, symptoms assessment, and ECOG performance score
2. Blood draw for CBC, chemistry panel, serum PSA and PAP (to be obtained prior to administration of immunization/GM-CSF)
3. Immunization/GM-CSF and post-treatment monitoring as described above

F. End of initial vaccination series evaluation (2 weeks after sixth vaccination, i.e. month 3 (day 85 +/- 2 days)

1. Physical examination, including vital signs, symptoms assessment, and ECOG performance score.
2. Blood draw for CBC, chemistry panel, serum PSA and PAP (to be obtained prior to administration of immunization/GM-CSF)
3. 10 ml peripheral blood (red-top tubes) for sera to evaluate antibody responses, and 100 ml peripheral blood (green-top heparinized tubes) for T-cell response evaluation
4. Immunization/GM-CSF and post-treatment monitoring as described above
5. BIOMARKER COHORT ONLY: NaF PET/CT (can be performed +/- 14 days of this 3-month immunization/GM-CSF visit). NOTE: This study is for research purposes only and will not be used for clinical response evaluation or treatment decisions. This study will be performed only at designated sites (UWCCC and JHU).

G. Day 127 (+/- 10 days) – BIOMARKER COHORT ONLY

1. Blood draw for serum PSA and PAP (does not require a clinic visit; the purpose of this draw is to provide PSA values to determine a PSA doubling time

corresponding with the 3-6 month period over which NaF PET/CT scans are obtained).

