H. Quarterly booster immunizations (every 3 months (days 169, 253, 337, 421, 505, 589, each +/- 7 days) – beginning at month 6 immunization – up to 6 total (to complete 2-year treatment course)

1. Physical examination, including vital signs, symptoms assessment, and ECOG performance score
2. Blood draw for CBC, chemistry panel, serum PSA and PAP (to be obtained prior to administration of immunization/GM-CSF)
3. Immunization/GM-CSF and post-treatment monitoring as described above
4. CT scan abdomen/pelvis and bone scan – performed prior to second quarterly booster/treatment (i.e. 6 months after first immunization/treatment), and every 6 months (every other visit) thereafter. Can be performed +/- 7 days of study visit.
5. 10 ml peripheral blood (red-top tubes) for sera to evaluate antibody responses, and 100 ml peripheral blood (green-top heparinized tubes) for T-cell response evaluation (Quarterly for 1st year following initial series, 3 time points, only)
6. BIOMARKER COHORT ONLY: Leukapheresis (~1.0 blood volume, 100 mL collection) at month 6 evaluation for T-cell response evaluation (can be performed +/- 14 days of this study visit). This leukapheresis replaces 100-ml peripheral blood requirement in 10.G.5 above for the month 6 time point. NOTE: As an alternative to leukapheresis, 200 ml peripheral blood (green-top heparinized tubes) can be collected. This is for T-cell response evaluation and immune biomarker studies.
7. BIOMARKER COHORT ONLY: NaF PET/CT (to be performed +/- 7 days of the 6-month immunization/GM-CSF visit). NOTE: This study is for research purposes only and will not be used for clinical response evaluation or treatment decisions. This study will also be performed only at designated sites (UWCCC and JHU).

I. End of Study Visit or 2-year (Day 672 +/- 7 days) Off-Study Visit

1. Physical examination, including vital signs, symptoms assessment, and ECOG performance score
2. Blood for CBC, chemistry panel, serum PSA, serum PAP
3. 10 ml peripheral blood (red-top tubes) for sera to evaluate antibody responses, and 100 ml peripheral blood (green-top heparinized tubes) for T-cell response evaluation. [Note: these specimens not required if subject off study prior to 12 month visit. However, these will continue to be drawn at quarterly intervals up to 12 months after screening/randomization in all subjects, even if off-study prior to 12 months.]

J. Follow up for Subjects Who Come Off Study Prior to 12-Month Visit

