The detection of antigen spread to other prostate associated antigens, and the identification of specific antigens recognized, will be analyzed descriptively. In addition, logistic regression analysis will be conducted to evaluate whether antigen spread is associated with the generation of PAP-specific immune responses elicited as a result of treatment. The dependent variables will be the detection of IgG responses to ≥ 1 “off-target” antigen at 6 months (and not present pre-treatment) while treatment arm and 6-month PAP-specific immune responses (no vs. yes) will be included as covariates. The results will be reported in terms of odds ratios and the corresponding 95% confidence intervals.

Results from the QTBI analysis will be used to determine whether individuals with identifiable bone lesions exhibit early disease progression (within 1 year) by standard bone scintigraphy and/or CT scans, and whether the time to metastatic disease is different with respect to treatment group. Specifically, the association between baseline QTBI parameters and time to disease progression will be evaluated using Cox proportional hazard analysis. Analogously, logistic regression analysis will be conducted to evaluate presence of lesions detected by NaF PET/CT at baseline is associated with early disease progression (within 1 year) rate.

Furthermore, % changes in QTBI parameters from the baseline to the 3 and 6 months assessment will be calculated and summarized in terms of means, standard deviations, medians and ranges, stratified by treatment arm. A linear mixed effects model with subject specific a random effects will be used to evaluate the association between changes in QTBI parameters and changes in PSA doubling time.

Due to the exploratory nature of the biomarker evaluations proposed in this trial, no adjustments will be made for multiple comparisons. Except for the primary endpoint which will be compared

at the one-sided 5% significance level, all other comparisons will be made using a two-sided test at a significance level 0.05 without adjustment for multiplicity. Data analysis will be conducted using SAS software (SAS Institute, Carey NC), version 9.3 or greater.

14. Administrative Considerations

A. Specimen Handling

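### In the biomarker cohort, the month-6 leukapheresis window spans a booster, so it pools samples taken about 9 to 13 weeks after a dose with samples taken within two weeks of one

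*Combined protocol and SAP*

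**What the plan says.** **Dosing around month 6.** Section 10.F places the end-of-series visit "2 weeks after sixth vaccination, i.e. month 3 (day 85 +/- 2 days"), and its item 4 reads "4. Immunization/GM-CSF and post-treatment monitoring as described above", so a dose is given at Day 85. The schema labels that visit bV7. Section 10.H then schedules quarterly boosters "every 3 months (days 169, 253, 337, 421, 505, 589, each +/- 7 days"), "beginning at month 6 immunization". Item 3 of that section gives an injection at each of these visits.

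**Month-6 cell sample.** Section 10.H item 6 applies to the biomarker cohort only. The leukapheresis "can be performed +/- 14 days of this study visit" and replaces the 100 mL T-cell blood draw. A 200 mL draw is allowed instead.

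**Order relative to injections.** Section 10.H item 2, like the matching items in 10.E and 10.F, requires CBC, chemistry, PSA and PAP blood to be drawn before dosing. Items 5 and 6, which cover the immune samples, carry no such condition. The only ordering rule for immune samples is at screening, before tetanus (Section 10.B, biomarker schema footnote m, Appendix B).

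**Uses of the month-6 cells.** Section 11.B.4 runs the trans-vivo DTH (tvDTH) assay on cells from before treatment and from 6 months. In Section 13, the antigen-spread logistic model states that treatment arm and "6-month PAP-specific immune responses (no vs. yes) will be included as covariates".

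**The concern.** A sample taken before the month-6 injection shows what persists from earlier doses. A sample taken up to two weeks after it shows the response to a fresh boost. The protocol's own prior experience (Section 4) treats these as different quantities. The phase I/II immune endpoint was the response "detectable two weeks following the final immunization", and in the one patient given later boosters, "booster immunizations were able to augment PAP-specific CD4+ and CD8+ proliferative T cells". The same section links immunity persisting after immunization to favourable PSA doubling-time changes.

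Three consequences follow if the two kinds of sample share one label:

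- The month-6 tvDTH result and the yes/no PAP response at 6 months depend partly on when the procedure was booked.
- In the antigen-spread model, the outcome comes from month-6 serum (Section 11.B.5), drawn separately under item 5. Outcome and covariate for one patient can fall on opposite sides of a booster.
- Patients leave study at metastasis (Section 8.B) but still give blood at Day 169 (Section 10.J). They receive no month-6 booster, so their sample cannot be post-boost, while samples from patients still on treatment can be. If a boost raises the measured response, this could produce an association between response and remaining metastasis-free that is partly an artefact of timing.

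**Working it through.** The plan states no figure for time since last dose, so the check is calendar arithmetic on its own visit days.

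**Inputs.** Dose at Day 85 +/- 2 (Section 10.F). Next dose at Day 169 +/- 7 (Section 10.H). Leukapheresis within 14 days either side of the month-6 visit (Section 10.H item 6).

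**Schedule check.** Sixth biweekly dose at Day 71: 71 + 14 = 85. Gap from Day 85 to Day 169: 169 - 85 = 84 days = 12.0 weeks, the same 84-day spacing as all later boosters.

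**Nominal days.** The window runs from 169 - 14 = Day 155 to 169 + 14 = Day 183.

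| Leukapheresis day | Last dose | Days since last dose |
|---|---|---|
| 155 | Day 85 | 155 - 85 = 70 (10.0 weeks) |
| 168 | Day 85 | 168 - 85 = 83 (11.9 weeks) |
| 169, before injection | Day 85 | 169 - 85 = 84 (12.0 weeks) |
| 170 | Day 169 | 170 - 169 = 1 |
| 183 | Day 169 | 183 - 169 = 14 |

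**With visit windows.**

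- Shortest pre-booster interval: visit at Day 162, sample 14 days earlier at Day 148, previous dose at Day 87. 148 - 87 = 61 days (8.7 weeks).
- Longest: visit at Day 176, sample that day before injection, previous dose at Day 83. 176 - 83 = 93 days (13.3 weeks).
- Post-booster interval: still 1 to 14 days, because the window is tied to the actual visit. A same-day sample after the injection is not excluded either.

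**Separation.** The two ranges do not overlap. The closest pre-booster and post-booster values differ by 61 - 14 = 47 days (70 - 14 = 56 on nominal days).

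**Does any other text close the gap?** Footnotes e, l and m of the biomarker schema, Section 10.J and Appendix B give windows, alternatives and volumes, but no order relative to the month-6 injection. Section 13 has no adjustment for time since last dose.

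**With a pre-dose rule.** All month-6 samples would lie 70 to 84 days after the Day 85 dose on nominal days, with no 1-to-14-day group.

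**The case against.** The strongest reply is that little depends on this sample. Section 13 defines the T-cell response at completion of treatment and compares response rates between arms without naming month 6. Blood is also drawn at months 3, 9, 12 and end of study. The antigen-spread outcome uses serum. Section 11.B.4 calls tvDTH not strictly quantitative, and Section 13 lists it only among baseline responses. All of this is exploratory, in 50 of 106 patients. These points stand and limit the weight of the concern, but they do not remove the mixture from the two month-6 uses that are named.

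A reader might infer that the window biases the comparison between arms, because only the vaccine arm is boosted with PAP. The documents do not support that. Both arms share the window and the trial is blinded, so scheduling should not depend on arm. A higher PAP response after a boost is a real vaccine effect. What becomes unclear is which quantity a pooled month-6 rate estimates.

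The booster evidence is also thin: one patient, boosted monthly and starting 18 months after the first series. It makes a timing effect plausible but does not give its size after a single quarterly booster.

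At Day 85 the immune blood is listed ahead of the injection, at a visit defined by its two-week lag. Post-dose sampling is not the natural reading there, and a change to 10.F would be for consistency only.

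**Conclusion.** The concern holds for the biomarker cohort. As written, the plan allows month-6 cells to be taken either about 61 to 93 days after the Day 85 dose or 1 to 14 days after a booster, and treats them as one time point. The likely result is extra noise in the month-6 tvDTH assay and in the 6-month PAP-response covariate. There is a secondary risk of distorted response-outcome associations, through patients off treatment by month 6. The primary metastasis-free survival analysis is not touched.

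This rests on the Day 85 dose having been given as Section 10.F item 4 states; a missed dose would lengthen the pre-booster interval. The documents do not show how many samples fall on each side, so the size of the effect on any response rate cannot be stated.

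Two stronger readings are not supported:

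- A reader might infer that timing differs by site, because leukapheresis and the 200 mL draw have different availability. Footnote l limits the site rule to baseline and opens the 200 mL draw to UWCCC at 6 months. Item 6 does not say whether that draw shares the 14-day window.
- A reader might take month 6 as the trial's main immune measurement. The Section 13 response definition points to the end of treatment instead.

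**What to change.** - **Section 10.H item 6:** require the month-6 leukapheresis or 200 mL draw within 14 days before, or on the day of, the month-6 visit, and in every case before that visit's injection. This also settles which window applies to the 200 mL alternative.
- **Section 10.H item 5 and, for consistency, Section 10.F item 3:** add the pre-administration condition that item 2 of each section already carries for its own blood draws.
- **Samples already collected:** Section 14.B has samples coded with the draw date, so days since last injection can be derived from existing records. Flag post-booster samples and repeat the month-6 analyses without them as a sensitivity analysis. With about 25 vaccinated patients in this cohort, a formal split into two groups would be too small to interpret.

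**Cost.** The change is to wording, and dosing is unchanged. The scheduling span falls from 28 days to 14, and the 200 mL draw remains available. A post-boost reading at month 6 is given up, but the Day 85 blood already samples at two weeks after the sixth dose.

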Prostate cancer is the most common tumor among men, and the second leading cause of male cancer-related death in the United States [1]. Despite advances in screening and early detection, nearly 30,000 U.S. men are estimated to have died as a result of prostate cancer in 2007 [1]. Treatment with surgery and radiation remain effective for presumed organ-confined disease, however approximately one third of these patients will have progressive or metastatic disease at 10 years [2]. A retrospective review of patients with prostate cancer treated with prostatectomy demonstrated that with evidence of a rise in serum PSA after definitive therapy, so-called “stage D0” disease, patients ultimately developed radiographically apparent metastatic disease within a median of 8 years [3]. Prostate cancer, once it becomes metastatic, is not curable and is generally initially treated with androgen ablation therapy with an average three-year progression-free survival before the disease becomes refractory to hormonal manipulations. Many patients with this stage D0 disease (rising PSA after definitive treatment, and without evidence of radiographically-apparent metastatic disease) are often treated with androgen deprivation. Androgen deprivation in this context could be by orchiectomy or treatment with LH-RH agonists, with or without a nonsteroidal anti-androgen. Observation is also an option, in particular given the potentially long natural history of this stage of disease. In patients with rising serum PSA after definitive therapy, without radiographic evidence of metastases and not on androgen deprivation therapy, the rate of rise of the serum PSA blood test (PSA doubling time, PSA DT) may be the most important prognostic indicator. Several recent retrospective reports have highlighted that patients with rapid PSA DT in this stage of disease have a markedly shorter time to the development of metastases and death [4, 5, 6, 7]. In a prospective analysis, the most important contributors to metastatic disease progression were the PSA DT, the original Gleason score, and the baseline PSA at the start of prospective monitoring [5]. Consequently, this clinical stage D0 disease represents a high-risk population of patients for whom there is not a standard therapy, for whom observation is typically employed, and whose progression-free survival can be estimated based on known factors, including PSA DT [7]. This represents a population for whom new treatments without the side effects associated with androgen deprivation could be evaluated.

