of antigen to T-cells [47]. In human studies, soluble GM-CSF has been used as a vaccine adjuvant for a hepatitis B vaccine. In this phase I study, doses of 20-80 µg GM-CSF were administered just prior to and at the same site as the hepatitis B protein vaccination. Of 81 subjects treated with GM-CSF, 15 developed anti-HBs after only 1 injection (10 had protective titers) while only 1 of 27 patients vaccinated without GM-CSF produced a weak and transient antibody response [48]. GM-CSF-expressing autologous cells have also been demonstrated in murine and human studies to be able to elicit immune responses to autologous antigens [49, 50, 51]. GM-CSF has also been demonstrated to be a potent adjuvant for plasmid DNA vaccines. Several groups have demonstrated in animal models that plasmid DNA encoding GM-CSF can enhance the immune response generated to a target antigen when co-immunized with plasmid DNA encoding the antigen [39, 52, 53]. The use of plasmid DNA encoding GM-CSF, however, carries a theoretical risk of eliciting an immune response to GM-CSF [54] or to other self proteins. In addition, GM-CSF alone, given at higher doses in more frequent schedules, has been investigated as a treatment for early stage and castrate-resistant prostate cancer [55, 56, 57]. Treatment with GM-CSF alone has been associated with increases in circulating monocytes and lymphocytes, and has been associated with long-term disease control in patients with clinical stage D0 prostate cancer [58]. For all of these reasons, the current trial will investigate the use of soluble GM-CSF as an adjuvant for the DNA vaccine, compared with GM-CSF only as a control group.

D. NaF PET/CT and Quantitative Total Bone Imaging (QTBI)

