The primary efficacy endpoint is the 2-year metastasis-free survival probability. Slovin et al reported a median MFS of 19 months in patients with rising prostate-specific antigen values following surgery or radiation therapy [5]. Based on these results, it is anticipated that the 2-year MFS rate in the placebo/GM-CSF arm will be approximately 40%. For the DNA vaccine encoding PAP with rhGM-CSF arm, it is anticipated that the 2-year MFS rate is at least 70%, based on promising efficacy results from the previous phase I/II trial with the same DNA vaccine in high-risk stage D0 prostate cancer patients. A sample size of 56 subjects (28 on each arm) with stage D0 prostate was initially proposed for this trial, and this cohort of patients (accrued at UW and UCSF sites only) is specifically being evaluated under the original DOD sponsor. An additional cohort of 50 subjects (25 patients on each arm) with the same inclusion/exclusion criteria will be treated in identical fashion, but will undergo further evaluation as described above for the biomarker analyses. This cohort of subjects is not under the oversight of the original DOD sponsor, rather a separate corporate sponsor (MVI). Hence, the proposed total sample size for this extended trial is 106 subjects (53 per arm). There will be no interim analysis conducted after the initial cohort of 56 patients has been accrued. The sample size of the original study (56 patients) was chosen to detect the anticipated difference of 40% versus 70% with 80% power at the relatively large one-sided 10% significance level. For a phase II trial such as the proposed study, it is desirable to limit the type II error to be 10% or less. The proposed total sample size 106 of the extended trial will be adequate to warrant sufficient power (>90%) to detect the anticipated difference of 40% versus 70% in the 2-year MFS rate at the one-sided 5% significance level, assuming an attrition rate of up to 15%. After the last subject is randomized, each subject will be followed for at least 24 months for metastasis. The following table shows the attainable power levels to detect various differences in the 2-year MFS rates between the two study arms at the one-sided 5% significance level, assuming a sample size of 53 subjects per arm with an attrition rate of 15%.

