No benefits are guaranteed. It is hoped that individual patients treated with the DNA vaccine will derive a clinical response indicated by an increase in serum PSA doubling time and a prolonged time to PSA recurrence and the development of metastatic disease. Moreover, GM-CSF alone has been investigated as a treatment for prostate cancer. Consequently, it is possible that patients treated with GM-CSF alone will also derive clinical benefit from treatment with GM-CSF. While no direct benefit is guaranteed, the results from this trial will guide the direction of future vaccine trials targeting PAP or potentially other antigens for the treatment of prostate cancer. Thus, it is hoped that future patients will benefit from research participation in the current study.

17. Study Data Management and Procedural Issues

A. Study Enrollment Procedures – Recruitment and Informed Consent Process:

A.1. For Subjects enrolled at UWCCC

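### Does the 40% planning rate for the GM-CSF control arm overstate the power by leaving out any effect of GM-CSF itself?

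*Combined protocol and SAP*

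**What the plan says.** Section 13 (Power Calculation) relies on a cited study that "reported a median MFS of 19 months in patients with rising prostate-specific antigen values" after surgery or radiation. From this, "it is anticipated that the 2-year MFS rate in the placebo/GM-CSF arm will be approximately 40" per cent. The vaccine arm is put at 70% or more, "based on promising efficacy results from the previous phase I/II trial with the same DNA vaccine". Section 4 reports that in that earlier trial "GM-CSF was co-administered as a vaccine adjuvant with each immunization".

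Two other places treat GM-CSF as possibly active. Section 2.C says GM-CSF alone has been studied at higher doses and on more frequent schedules, "and has been associated with long-term disease control in patients with clinical stage D0 prostate cancer [58". Section 16.B says "it is possible that patients treated with GM-CSF alone will also derive clinical benefit from treatment with GM-CSF".

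The enlargement from 56 to 106 patients is justified in Section 13 by the remark that "it is desirable to limit the type II error to be 10% or less", with power above 90% for 40% versus 70%, one-sided 5%, allowing 15% attrition. The text after the power table attaches conditions to the 91%: a true control rate no higher than 40% and a true vaccine rate above 70%. The table varies the control rate from 0.38 to 0.44 and the vaccine rate from 0.66 to 0.74.

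**The concern.** The two planning rates seem to be on different footings. The 40% comes from a cohort for which no GM-CSF is mentioned. Section 1 cites the same reference as a prospective analysis whose prognostic factors were PSA doubling time, Gleason score "and the baseline PSA at the start of prospective monitoring [5". With an exponential curve (an assumption), a 19-month median gives 0.5^(24/19) = 41.7% at 24 months, so 40% holds no upward allowance. The 70% is projected from a regimen that contained GM-CSF. On this reading the 30-point difference contains vaccine plus GM-CSF, while the randomized contrast isolates the vaccine.

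Power would be at stake. If GM-CSF alone raises the control rate and the vaccine arm still reaches only 70%, the difference shrinks and the target of a type II error of 10% or less is missed. Section 2.E also assumes a median time to progression of about 2 years in higher-risk patients. Read literally, that implies about 50% at 2 years rather than 40%.

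**Working it through.** **Inputs from Section 13.** 53 per arm, 15% attrition, so n = 53 × 0.85 = 45.05 per arm; one-sided 5%, z = 1.645; rates 0.40 and 0.70.

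**Plan's own figure.** Normal approximation with unpooled variance:

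power = Φ{(p₂ − p₁) / √[(p₁q₁ + p₂q₂)/n] − 1.645}

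For 0.40 versus 0.70: √[(0.24 + 0.21)/45.05] = 0.0999; 0.30/0.0999 = 3.00; Φ(1.357) = 0.913. The plan prints 0.91, and all 20 table cells agree within 0.010. A log-rank calculation with 40.5 events and hazard ratio ln 0.70/ln 0.40 = 0.389 also gives 0.913.

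**Allowing for GM-CSF.** The documents give no effect size. Hazard ratios of 0.9 to 0.75 for GM-CSF alone are assumed here for illustration and applied as control rate = 0.40^HR. The answer then depends on what is held fixed in the vaccine arm:

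| GM-CSF HR (assumed) | Control rate | Power, vaccine fixed at 70% | Power, hazard ratio 0.389 kept (vaccine rate) | Power, 30-point gap kept (vaccine rate) |
|---|---|---|---|---|
| 1.0 | 0.400 | 0.91 | 0.91 (0.700) | 0.91 (0.700) |
| 0.9 | 0.438 | 0.83 | 0.89 (0.725) | 0.92 (0.738) |
| 0.8 | 0.480 | 0.70 | 0.87 (0.752) | 0.93 (0.780) |
| 0.75 | 0.503 | 0.62 | 0.85 (0.765) | 0.93 (0.803) |

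**How much the plan already shows.** ln 0.44/ln 0.40 = 0.896, so the table's last control row corresponds to a GM-CSF hazard ratio of about 0.90. It prints 0.82 against 0.70, where the formula gives 0.826. The 0.42 row prints 0.87. The mild end of the range is therefore already disclosed; only control rates above 0.44 lie outside the table. With the vaccine fixed at 70%, power reaches 0.80 at a control rate of about 0.449 (HR about 0.87). At 50%, the literal reading of Section 2.E, it is 0.63.

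**Sample size on the most adverse scale.** n per arm = (1.645 + 1.2816)² (p₁q₁ + p₂q₂)/(p₂ − p₁)², rounded up, divided by 0.85, rounded up and doubled. At 40/70: 42.8, then 43, then 51 per arm, 102 in total, in line with the planned 106. At HR 0.9, 0.8 and 0.75 the totals are 138, 194 and 240. Each depends wholly on the assumed hazard ratio.

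**The case for a change.** The strongest case for acting is that fixing the vaccine rate at 70% is a coherent reading. The evidence behind it came from patients who all received GM-CSF, and the protocol itself considers GM-CSF possibly active in this disease stage. The planning point also has little slack: the formula needs 102 patients and the plan has 106. Even 41.7% against 70% gives 0.88. At HR 0.75, a vaccine arm that reaches 70% would be missed with probability 1 − 0.62 = 0.38. A sentence naming the GM-CSF assumption would cost almost nothing.

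Part of this stands. Section 13 does not say what the 40% assumes about GM-CSF, and the stated power is sensitive to the control rate. Three things limit it:

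- The size is not in the documents. Section 2.C ties the GM-CSF evidence to higher doses and more frequent schedules, whereas this trial gives it every two weeks and then every three months. An effect near zero is as compatible with the text as HR 0.75.
- The 70% is a projection. Section 4 reports safety, T-cell responses and a change in median PSA doubling time from 6.5 to 8.5 months after six immunizations, but no 2-year MFS. It cannot be shown to be a measured rate with a GM-CSF share inside it. The present regimen also adds quarterly boosters, and the plan says at least 70%.
- The documents do not say whether the cohort with the 19-month median was untreated, so the mismatch in footing is inferred.

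The 2-year median in Section 2.E is looser background wording. It does not involve GM-CSF, and the power calculation does not use it.

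**Conclusion.** No change is needed. The stated power is right for the rates it names, is expressly conditional on them, and comes with a table that shows how it falls as the control rate rises. Beyond that table, the result runs from a substantial loss (0.70 to 0.62, vaccine held at 70%) through a small one (0.87 to 0.85, hazard ratio kept) to none (0.93, 30-point gap kept). Nothing in the documents chooses among these or supplies a GM-CSF effect. A larger trial of 138 to 240 patients would rest on a hazard ratio that the plan does not contain.

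Writing the GM-CSF assumption into Section 13 would record a planning premise without altering enrolment, endpoint, test or result. The choice of control protects the inference: both arms receive GM-CSF, so the comparison isolates the vaccine and the type I error does not depend on the 40%. If the control arm does better than planned, this will be visible, because the primary-endpoint analysis already tabulates 2-year MFS and gives Kaplan-Meier estimates by arm. A null result can then be read against the observed control rate. For a phase II trial with a fixed budget of patients, this is a fair trade-off. The conclusion assumes the normal approximation that matches the plan's table and proportional hazards for shifting the control rate.
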